7.2.2 Randomization

We will randomize by grade levels within each school to receive either one-time universal screening (via PHQ-9) or targeted screening (current SAP process). For the 8 schools included in the study, 4 schools (50%) will be randomized such that students in 9th and 11th grades will receive universal screening and students in 10th and 12th grades will receive targeted screening, and 4 schools (50%) will be randomized such that students in 9th and 11th grades will receive targeted screening and students in 10th and 12th grades will receive universal screening. Randomization will be done only for students whose parents do not signal an unwillingness to participate in the study (“opt out”). Students and study personnel will not be blinded to randomized group at each school site. Randomization will be done by grade level primarily for pragmatic reasons because many PA health-based screenings are grade-specific (e.g. hearing screen in 11th grade) and screenings for a grade occur at the same time. The study will be conducted within schools, but it is not a cluster randomized study, in which an entire school (cluster) is assigned to one of the study groups. A cluster randomized study was considered but ultimately not pursued because randomization within schools controls for (1) within-school (community) factors that may contribute to higher or lower rates of SAP referral, (2) differences in school sizes, and (3) potential differences in rates of parental opt out among schools. These benefits were balanced against the concern of potential contamination between study groups, whereby those in the targeted screening group may benefit from the school-wide push to conduct universal screening.

7.2.3 Universal MDD Screening Arm (Intervention – Treatment)

Students randomized to the universal screening arm will complete a PHQ-9. This screening tool includes nine close-ended questions with a scoring system ranging from 0 to 27. The PHQ-9 screens will be administered on an iPad with an internet connection which allows direct entry of the results in REDCap. To prevent the duplication of unique study IDs, the study team will have entered all unique IDs into REDCap prior to the screening. A list of participant IDs will be provided to the school member present during the screening. Once the corresponding unique study ID has been entered, the study staff will give the iPad to the student to assent and complete the PHQ-9. This process will ensure that the correct study ID is used and prevent duplication of study IDs. Further, this will safeguard against any student from participating whose parent returned the opt-out letter. No names or other identifying information will be used. Paper copies of the assent and PHQ-9 will be available as a backup should problems arise with internet connectivity. The same measures will be taken to ensure no names or other identifying information is used or collected.

In order to immediately identify suicidal intent the survey will be set to flag positive questions in real time. When students have completed the PHQ-9 screen the REDCap survey will prompt them to hand the completed questionnaire to study staff, who will see a screen indicating a positive flag. Students with suicidal intent (question #9 any response besides “Not at all”) will receive immediate evaluation and referral to emergency care as per current school protocols. PA schools are required to have a plan to address suicidal students (Act 71). A suicidal participant identified during the screening would not be allowed to leave the screening area unless accompanied by appropriate school or research staff. This student would then proceed through the standard school pathway for managing a student with intentions of self-harm. To ensure school staff is comfortable to manage a student in crisis and that this persists beyond the period of the grant, at least 5 staff per school in addition to at least 4 Penn State research staff will complete online evidence-based suicide prevention training (Question, Persuade, and Refer [QPR] Suicide Triage Training). In addition, all school crisis plans will be carefully reviewed with staff following the training to ensure the steps are realistic and staff is comfortable to execute the plan.

The district identified, QPR trained staff member will be available at the time of screening. Study staff who are also QPR trained, will be present during the screening.

7.2.4 Targeted Screening Arm (Current Process – Control)

Students randomized to the targeted screening arm will complete their routine school-based screenings. Students will be followed through the academic year for SAP triage intakes initiated by the standard pathway (concern by teachers, nurse, parent, peer, or self-referral), any referrals and treatment engagement.

7.2.5 Sharing Screening Results

At 14 years of age, PA youth are eligible to consent to mental health services without parental consent, therefore, screening results will not be shared with parents. Those students with scores ≥ 11 (MDD screen positive) corresponding to moderate depressive symptoms will, however, proceed through the standard process for anyone referred by traditional means to a SAP triage interview. The student will either refer to appropriate community or school-based treatment or therapy (MDD identified) or SAP will determine no follow-up is needed. For those who are recommended to additional services by SAP, treatment engagement will be tracked per current SAP process. As per current school policy, students with suicidal feelings will receive immediate referral to emergency care and parents will be notified by the school.

7.3 Duration of Participation

The student's participation is limited to the 5 minutes it takes for them to participate in the screening process.

8.0 Subject Numbers and Statistical Plan

8.1 Number of Subjects

The 8 schools to be included in the study have an estimated total enrollment of approximately 9650 students. The overall rate of parental opt out is expected to be around 20%, resulting in approximately 7720 students included in the study. We assumed a 15% attrition rate for students who move, drop out of school, or opt out later in the school year. Thus, the study is expected to include 6550 students.

8.2 Sample size determination

A total of 3275 students in each randomized group (an overall sample size of 6550) yields >99% statistical power to detect a difference of 3% versus 6% using a 2-sided test conducted at a Type I error rate of 5% in a mixed effect logistic regression model.

8.3 Statistical methods

The principles of intention-to-treat (ITT) will be used for all statistical analyses related to primary and secondary aims. For the primary aim comparing universal to targeted screening, the statistical analysis will be conducted using a mixed effects logistic regression model. The primary outcome, MDD composite, will be an indicator whether a student was screen positive (or concerns raised in the targeted screening arm), identified as having MDD and subsequently engaged in treatment (1=yes, 0=no). The model will include a fixed effect for randomized group (0=targeted screening, 1=universal screening) and a random effect for school. The random effect accounts for correlation among students enrolled within the same school. The primary parameter of interest will be the log odds of MDD composite in the universal screening group compared to the targeted screening group. Statistical significance of the log odds will be assessed using a 2-sided Wald test. Point estimates for the odds ratio along with a 95% confidence interval will be reported.

For the analysis of Hypotheses 2 and 3 (Objective 1) evaluating universal screening and targeted screening by selected subgroups, the same mixed effects logistic regression modeling framework will be used, but the model will be extended by including a fixed effect for subgroup and an interaction effect for subgroup by randomized group. The interaction term will be the parameter of interest. A significant interaction term indicates that rates of MDD treatment engagement for universal versus targeted screening differ by subgroup level (e.g. female vs. male). For the analysis of Hypotheses 1 through 4 (Objective 2) that evaluates universal screening and targeted screening based on school SAP data, we will have only 32 total data points (4 grades in each of 8 schools). Mixed-effects linear (continuous outcomes) and logistic regression (binary outcomes) will be used, as appropriate, with a fixed effect for randomized group and a random effect for school. The parameter of interest will be the log odds for the universal compared to the targeted screening group. Due to the smaller sample size used for these outcomes, these analyses will be considered to be primarily hypothesis-generating. Potential mediating variables (socioeconomic status, rural vs. urban location, school size, ratio of guidance counselors to students and availability of school-based mental health services) will be evaluated for both the Objective 1 and 2 hypotheses.

Additional secondary outcomes will include MDD screen results, MDD concern prompting Student Assistance Program triage, MDD identification and MDD treatment engagement analyzed individually (rather than as part of MDD composite). Finally any suicidal adolescents (suicidal thoughts [positive response to PHQ-9 item 9], attempts and completed) will be analyzed as a secondary outcome.

We need to collect data for individuals for 3 main reasons. First, we expect approximately 20% of students to opt out from the study, with opt out rates varying by grade. Aggregate data would necessarily include outcomes for students who are not enrolled in the study. This is particularly problematic for the universal screening group because students who opt out will not be offered the depression screening tool (PHQ-9). Second, we need to obtain gender and race/ethnicity to conduct important planned secondary analyses (subgroup analyses) that will examine efficacy of universal screening by these groups. In particular, we expect that females and minority students will have much higher rates of major depression disorder identified in the universal screening group. Third, in the universal screening group, we will be able to link responses to the PHQ-9 to outcomes, which will allow for estimation of important measures such as the false positive rate of the PHQ-9 (score ≥ 11 , but SAP process determines no further referrals are needed). These measures will inform decision-making regarding the potential for implementation of the intervention (in other schools) should the results of the trial ultimately show efficacy.

Efforts will be made to ensure completeness of data where possible, but missing data will occur for a number of anticipated reasons. First, a student may move during the course of the school year to another school district or drop out from school entirely. No data will be collected after this time point. Second, parents may opt out their child from the study at any time during the school year. Third, students who turn 18 during the school may decide to opt out of the study themselves. In both of these instances, data from SAP referrals that occur after opting out will not be collected for purposes of the study. Fourth, during the one-time universal screening phase, students may decide to leave data forms incomplete, including the PHQ-9. To decrease these instances, the PHQ-9 will be taken on an iPad program and the survey will alert if the form is left incomplete.

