2.3 Study Rationale

Rates of major depression are rising among US adolescents paralleled by a rise in the rate of adolescent suicides. The most recent data indicates that 1 in 8 adolescents (12.5%) experienced an MDD episode in the past 12 months.¹ From 2005-2014 a significant increase in MDD episode trends was observed for all racial and ethnic groups except Non-Hispanic Blacks who demonstrated a smaller, statistically nonsignificant increasing trend.⁶ The most striking increase in MDD trends was for females across all racial and ethnic groups. Adolescent females demonstrated rates of MDD episodes over 3 times that of males (19.5% vs. 5.8%).^{1,6} Some authors have suggested that adolescent females have increased exposure to depression risk factors including cyberbullying, mobile phone use and texting.⁶ Along with

the rise in MDD episodes, adolescent females have demonstrated a significant rise in emergency department visits for nonfatal self-inflicted injuries with rates since 2009 increasing by 19% annually from 110 in 2009 to 318 per 100,000 in 2015.¹² Self-inflicted injury is one of the strongest risk factors for suicide, and the suicide rate for female adolescents reached its highest in the past 40 years according to 2017 Centers for Disease Control and Prevention data.^{13,14}

Adolescent MDD has negative effects on academic performance, with increasing severity of depressive symptoms linked to a lower grade point average as well as subjective assessments of increased school workload and concentration difficulties. Adolescents with untreated MDD experience poorer interpersonal relationships, lower self-esteem, social isolation, and increased risk-taking behaviors including substance use, as well as multiple physical and mental health comorbidities in adulthood.^{7,8,15-}

¹⁷ For 60-90% of adolescents, symptoms of a MDD episode may remit within in a year. The larger problem is that 50-75% of these adolescents will develop subsequent MDD episodes within 5 years, resulting a chronic or relapsing disorder.¹⁸ Studies also suggest that recovery is not complete between episodes, with most individuals reporting residual symptoms or impairment.¹⁸

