1.0 Objectives

1.1 Study Objectives

OBJECTIVE 1. Partnering with 14 PA public high schools (letters of commitment obtained for all 14 high schools) serving an estimated 12,582 predominantly minority, rural, urban, and/or low socioeconomic status (SES) students, we will conduct a randomized controlled trial, with student randomization by grade, to compare the effectiveness of universal school-based screening for adolescent major depressive disorder (MDD) versus the existing process of targeted screening based on concerning behavior.

- *Hypothesis 1: Universal screening will increase the number of adolescents with MDD screened, identified and engaged in treatment (MDD composite).*
- *Hypothesis 2 (Moderating): Universal screening will increase the historically poorer rates of MDD screening, identification and treatment engagement for females*
- *Hypothesis 3 (Moderating): Universal screening will increase the historically poorer rates of MDD screening, identification and treatment engagement for rural adolescents*

OBJECTIVE 2. Analyze the impact of MDD screening on secondary outcomes currently collected by the school's Student Assistance Program (SAP) and the school district. These data will be obtained in aggregate by grade level at each participating school (a total of 64 data points for each item; 4 grades x 14 schools, see note below re: PCORI). Please note, secondary outcomes may no longer be available due to COVID-19 school closures and cancellation of state standardized testing.

- *Hypothesis 1. Standardized test scores (e.g. Keystone exams, PSAT, SAT, ACT) will improve in school populations with universal MDD screening secondary to earlier identification, treatment referral and engagement.*
- *Hypothesis 2. Student school policy violations and suspensions will remain unchanged among school populations with the universal MDD screening approach.*

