8.2 Sample size determination

A total of 4,820 (estimated) students in each randomized group (an overall sample size of 9,640 [estimated]) yields >99% statistical power to detect a difference of 3% versus 6% using a 2-sided test conducted at a Type I error rate of 5% in a mixed effect logistic regression model.

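### Objective 2 compares grades on a single trial-year aggregate with no prior-year value; adding one where obtainable is a cheap, minor-priority gain in precision

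*Combined protocol and SAP*

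**What the plan says.** The file holds two protocol versions, one for 8 schools and a later one for 14. They agree on the points that matter here.

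- **Objective 2 data.** Section 1.1 describes "secondary outcomes currently collected by the school's Student Assistance Program (SAP) and the school district", obtained in aggregate by grade at each school. The 8-school version counts 32 values. The 14-school version states 64.
- **Objective 2 model.** Section 8.3 specifies linear or logistic mixed models "with a fixed effect for randomized group and a random effect for school". School-level variables such as socioeconomic status, counselor ratio and mental health services are to be evaluated as mediators. No prior-year value appears there or in the endpoint lists of Section 1.3. The section labels these analyses hypothesis-generating because the sample is small.
- **Allocation.** Under Section 7.2.2 two grades of each school get universal screening and the other two get targeted screening.
- **Primary model.** Section 8.3: "The model will include a fixed effect for randomized group (0=targeted screening, 1=universal screening) and a random effect for school". Sex is collected for each enrolled student (Section 1.3). It enters only the subgroup model, as a main effect and an interaction.
- **Limits already stated.** The 14-school version warns in Sections 1.1 and 1.3 that the secondary outcomes may be lost to COVID-19 closures. Section 7.1 records that the year 2 intervention stopped in March 2020, when in-person teaching ended.

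**The concern.** With two grades per arm in every school, differences between schools cancel from the comparison. What remains is variation between grades of one school. One figure per grade cannot separate a lasting peculiarity of, say, one school's 10th grade from an effect of screening. The listed school-level variables cannot help, because they are constant within a school. A common grade term would remove only the part of the grade pattern that all schools share. The natural covariate is the same item for the same school and grade one year earlier, and the plan does not ask for it.

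The stake is the width of the Objective 2 intervals. It bears most on the hypothesis that policy violations and suspensions will not change, because a no-change statement is only as good as its interval is narrow.

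**Working it through.** **1. The plan's own figure.** Section 8.2 of the 8-school version gives "A total of 3275 students in each randomized group (an overall sample size of 6550") and claims ">99% statistical power to detect a difference of 3% versus 6" per cent, "using a 2-sided test conducted at a Type I error rate of 5" per cent.

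- Log odds ratio = ln[(0.06 × 0.97)/(0.94 × 0.03)] = 0.7246.
- SE = √{[1/(0.03 × 0.97) + 1/(0.06 × 0.94)]/3275} = 0.1261.
- z = 0.7246/0.1261 = 5.745, and power is 99.99%.

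The claim reproduces with students treated as independent. With "A total of 4,820 (estimated) students in each randomized group" in the later version, power is higher still.

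**2. Number of Objective 2 values.** 8 schools × 4 = 32. In the later version 14 × 4 = 56, yet 64 is stated. Section 7.1 has 3 + 13 = 16 schools, and 16 × 4 = 64. The documents leave this unresolved, so all three counts are carried.

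**3. Detectable difference for Objective 2, continuous outcome.** The unit is the within-school SD between grades. N is the number of values, S the number of schools, and r the within-school correlation of the prior-year and trial-year figures. The documents do not give r, so a range is assumed.

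- SE = √(4/N) × √(1 − r²).
- Degrees of freedom = N − S − 1, less one when the covariate is in the model: 23, 41 and 47 without it; 22, 40 and 46 with it.
- Detectable difference = SE × the noncentrality giving 80% power in a two-sided 5% t test. That noncentrality is about 2.92, 2.87 and 2.86 for the three counts, and 2.93 for 32 values once the covariate is added.
- Example: 32 values and r = 0 give SE = √(4/32) = 0.354, and 0.354 × 2.92 = 1.03.

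| r | residual variance removed (r²) | 32 values | 56 values | 64 values |
|---|---|---|---|---|
| no covariate | – | 1.03 | 0.77 | 0.72 |
| 0.3 | 9% | 0.99 | 0.73 | 0.68 |
| 0.5 | 25% | 0.90 | 0.67 | 0.62 |
| 0.7 | 49% | 0.74 | 0.55 | 0.51 |

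**4. The no-change hypothesis.** The 95% half-width is t × SE.

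- No covariate: 2.07 × 0.354 = 0.73 SD (32 values) or 2.02 × 0.267 = 0.54 SD (56).
- r = 0.7: 2.07 × 0.252 = 0.52 SD or 2.02 × 0.191 = 0.39 SD.

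**5. Sex in the primary model.** Section 2.3 gives MDD episode rates of 19.5% in females and 5.8% in males, an odds ratio of (0.195/0.805)/(0.058/0.942) = 3.93. Assume a 50:50 sex split and hold the overall rates at 3% and 6%. From the expected information of the logistic model, adjusting for sex gives a log odds ratio of 0.7357, SE 0.1270 and z = 5.791.

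- Relative efficiency = (5.791/5.745)² ≈ 1.016. A stratified comparison that applies the 19.5:5.8 ratio to the risks gives z = 5.787, or about 1.015.
- Power stays at 99.99%. The SE of the log odds ratio does not fall (0.1261 to 0.1270).

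**The case against.** The case against giving this much weight is strong, and most of it stands.

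- **Availability is inferred.** The documents say the outcomes are collected now. They do not say that comparable prior-year figures by grade exist or would be released. A reader might infer that the data are there for the asking; the text does not go that far.
- **The correlation may be modest.** Last year's figure for the same grade comes from a different cohort, and the school effect already absorbs the between-school part. At r = 0.3 the gain is 0.04 SD. For the schools of study year 2, a pre-pandemic year would be paired with one cut short by COVID-19.
- **Some items may have no usable prior value.** Standardized tests, now Hypothesis 1 of Objective 2, and graduation may not give a comparable figure for every grade. Where the trial-year outcome is itself missing, a baseline repairs nothing.
- **The arithmetic is for continuous outcomes.** Section 8.3 sends binary outcomes to logistic regression, and the table does not carry over directly.
- **The plan is candid.** It already calls these analyses hypothesis-generating. That lowers the priority but does not remove the gain, since the stated reason is small numbers and a covariate addresses exactly that.

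Two stronger readings are tempting. One is that no model in Section 8.3 uses any baseline information. That is wrong, because the sex-subgroup model contains sex. The other is that leaving sex out of the primary model gives away real precision. The working shows about 1.5% and no smaller SE. Even at an assumed design effect of 6, power would move only from 65.0% to 65.7%. The 19.5:5.8 ratio also describes MDD episodes, not the composite, which further requires identification and engagement. Section 2.1 says females are less likely to be treated, so the sex contrast in the composite could be smaller.

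**Conclusion.** The point holds as a cheap improvement of minor priority. Objective 2 rests on one aggregate per school and grade with no prior-year value, in both versions. A prior-year covariate would lower the detectable difference by about 4 to 5% at r = 0.3, 13% at r = 0.5 and 28 to 29% at r = 0.7, whichever count of values is right. These figures rest on an assumed correlation, a continuous outcome, and districts being able to supply the data.

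No error rate or primary conclusion is affected, and Objective 2 would remain exploratory. Sex in the primary model is an optional addition with a negligible effect on power.

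**What to change.** In Section 8.3 and the data request:

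1. State, for each Objective 2 item, whether the aggregate for the same school and grade in the year before that school's trial year can be obtained, and request it. Using the same grade, not the same cohort, means that grade 9 can also have a value.
2. Where it is obtainable, pre-specify it as a covariate and report the unadjusted result as secondary.
3. State in advance that any item or school without a comparable prior-year value is analysed unadjusted.
4. Reconcile the number of Objective 2 values (56 or 64) with the number of schools.
5. Optionally, add sex as a fixed effect to the Objective 1 primary model. The odds ratio then becomes conditional on sex, and the text should say so.

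The cost is one more year in an existing request for aggregate, non-identifiable data, one degree of freedom in each Objective 2 model, possible missing values, and a few sentences in Section 8.3.
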